2.1. Overall Study Design and Plan

This is a randomized, double-blind, placebo-controlled, parallel group, multi-site study in non-hospitalized adult subjects who test positive for SARS-CoV-2 and have COVID-19 symptom onset within 5 days of randomization and who are not at high risk for progression to severe COVID-19. Subjects can be vaccinated or unvaccinated for COVID-19. Subjects with prior COVID-19 infection <90 days before enrollment and/or who received a COVID-19 vaccine dose <90 days before enrollment are excluded from trial participation.

[figure not shown]
Subjects will be randomized in a 1:1:1 ratio to receive either EDP 235 [REDACTED], EDP 235 [REDACTED], or placebo orally once daily for 5 days. Randomization will be stratified by age (≤ 50 years or 51 to 64 years) and by the duration of COVID-19 symptoms (≤ 3 days or >3 days and ≤ 5 days).

The study includes 4 periods:

- Screening period will occur from Day -1 to Day 1. Screening should be completed as soon as possible, and the subject will be randomized within 24 hours of signing the ICF. A subject will be considered enrolled at the time of randomization.
- Treatment period will begin with the first dose of study treatment on Day 1 and will conclude with the end-of-treatment (EOT) visit on Day 5.
- Follow-up period will begin following the last dose of study treatment and will conclude at the end of follow-up (EOFU) visit on Day 33 (28 days after the last dose of study treatment).
- Long-term follow-up period (LTFU) will begin at Day 34 and concludes at the end-of-study (EOS) visit at Week 24.

An overview of the study design is shown in **Figure 1**. Study site visits and assessments are detailed in the Schedule of Study Procedures ([Appendix 14.1](#)).

Figure 1: Study Design

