2.2. Study Endpoints

The study's primary, secondary, and exploratory objectives and their associated endpoints are displayed in **Table 1**.

Table 1: Study Objectives and Endpoints

| Objectives | Endpoints |
|-------------------------------------------------------------------------------------------------------------------------------------------------------------------|--------------------------------------------------------------------------------------------------------------------------------------------------------------------------------------------------------------------------------------------------------------------------------------------------------------------------------------------------------------------------------------------------------------------------------------------------------------------------------------------------------------------------------------------------------------------------------------------------------------------------------------------------------------------------------------------------------------------------------------------------------------------------------------------------------------------------------------------------------------------------------------------------------------------------------------------------------------------------------------------------------------------------------------------------------------------------------------------------------------------------------------------------------------------------------------------------------------------------------------------------------------------------------------------------------------------------------------------------|
| 
Primary Objective
 
 To evaluate the safety and tolerability of EDP 235 | 
Primary Endpoint
 
 Safety and tolerability of EDP 235 compared to placebo as assessed by, but not limited to, adverse events (AEs), clinical laboratory results, and vital signs through Day 33 |

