2.4. Dose Adjustment/Modifications

Dose modifications are not permitted for subjects in this study.

3. General Statistical Considerations

Continuous variables will be summarized using n, mean, standard deviation, median, 25th percentile (Q1), 75th percentile (Q3), minimum, and maximum values. The precision for continuous variables will be based on the precision of the data itself. The mean, median, 25th percentile, and 75th percentile will be presented to one more significant figure than the original results; the SD will be presented to two more significant figures than the original results; the minimum and maximum will be presented to the same level of precision as the original results.

Categorical variables will be summarized using frequency counts and percentages. Percentages will be presented to 1 decimal place. If the count is 0, the percentage will not be displayed. If the count equals the denominator, the percentage will be displayed as 100.

When **count data** are presented, the percentage will be suppressed when the count is zero to draw attention to the non-zero counts. A row denoted “Missing” will be included in count tabulations as needed to account for dropouts and missing values. The denominator for all percentages will be the number of subjects in the treatment group within the analysis set of interest, unless otherwise specified.

Baseline, unless otherwise specified, will be defined as the last non-missing measurement collected prior to dosing on the same date as the first dose of study treatment; if it is not available, the first measurement up to 2 hours post first dose of study treatment will be used. For

subjects who are randomized, but not treated, the baseline will be defined as the last non-missing measurement on or before the date of randomization. For height, weight and body mass index baseline will be defined as the last non-missing measurement collected on or before the date of the first dose of study treatment (without consideration of time). .

Study Day 1 is the calendar day that the first dose of the study treatment is administered. Subsequent study days are calculated as the date of assessment/event – date of the first dose + 1. If a subject is not treated, the date of randomization is used to define study day rather than the date of first dose. For assessments or events that occur before the first dose date, study day is calculated as the date of interest minus the first dose date.

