Unscheduled visits measurements will be included in the analysis as follows:

- Derivation of baseline and worst post-baseline measurements.
- Individual subject data listings as appropriate.

Unscheduled visits will not be included in the by-visit summary or analyses.

No additional analysis visit windowing will be done other than what is specified for Baseline and worst post-baseline above.

When there are multiple values within an analysis visit for laboratory assessments,, the worst value (and the latest value if applicable) will be used in the analysis. For graded labs, worst is defined as the highest grade and if there is more than one record of the same grade for a given analysis visit, the latest value will be selected for analysis. For non-graded labs, worst is defined as the smallest value for criteria below a certain threshold or the largest value for criteria above a certain threshold. If a subject has a value below the threshold and above the threshold, the value furthest from the threshold will be chosen.

For all other assessments, if there are multiple values within an analysis visit the latest record will be selected for analysis.

All diary data will be summarized based on the actual day.

Time-to-event variables are defined from the date of first dose.

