3.4.3. Intent-to-Treat-c (ITT-c)

The Intent-to-Treat (ITT-c) Population includes all subjects in the SAF Population with their SARS-CoV-2 status confirmed by central RT-PCR viral load at baseline \geq lower limit of quantification (LLOQ) and with at least one post-baseline primary efficacy measurement. Subjects will be analyzed as randomized.

The reasons for exclusion from the ITT-c population will be summarized by treatment group using the Safety population.

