3.4.4. Per Protocol (PP)

The Per Protocol (PP) Population includes all subjects in the ITT-c Population who do not have any protocol deviations that may unduly influence the primary efficacy outcomes as assessed by the sponsor prior to unblinding ([Section 4.2](#)) and do not meet any of the criteria shown below.

1. Compliance rate <80% ([Section 6.4.1. Extent of Treatment Exposure and Compliance](#))
2. Do not complete Day 33 Visit (discontinuation from study prior to Day 33 or incomplete follow-up at the time of analysis)

The reasons for exclusion from the PP Population will be summarized by treatment group and listed using the ITT-c Population.

Subjects will be analyzed in the treatment group that corresponds to the study treatment received during the study.

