4.1. Disposition

A subject will be considered to have completed the study after his/her attendance at the last planned study visit (Day 33 ± 1 day), or the last unscheduled visit (if any occur), as applicable. For each subject his or her study completion status (Yes/No) is recorded on the End of Study CRF.

The number of subjects randomized and in the SAF, ITT-c, PP, PK and IPK populations will be summarized using frequencies and percentages. All percentages will be based on the number of subjects randomized.

Subject disposition will be summarized by treatment group and overall, for all subjects who are randomized. A disposition of subjects includes the number and percentage of subjects for the following categories: subjects who were randomized, subjects who completed study treatment per protocol, subjects who discontinued study treatment early, subjects who completed the study, subjects who discontinued from the study early. All percentages will be based on the number of subjects randomized. The reasons for discontinuation of study treatment and study participation will also be summarized in this table.

The reason for discontinuation of study treatment or study participation may include any of the following:

- Adverse event
- Lost to follow-up
- Pregnancy
- Protocol deviation
- Study terminated by sponsor
- Withdrawal by subject
- Physician decision
- Death
- Other reason

Subject disposition data will also be presented in listings, including a listing by analysis population.

Screen failures were not included in the study database and will not be included in any SDTM or ADaM datasets. If required, a listing of screen failures from all screened subjects, including the inclusion or exclusion criteria that were not met, may be provided from vendor IRT data.

A separate listing of subjects that were randomized, treated and then found to meet exclusion or fail to meet inclusion criteria will be provided including the inclusion or exclusion criteria.

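### With no visit windowing and no early-termination visit, exit samples from subjects who leave before Day 33 would be analysed as Day 33, and any EOFU row for labs, vital signs or ECG would describe early leavers

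*SAP*

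**What the plan says.** Section 3 (General Statistical Considerations) sets the visit rule: "No additional analysis visit windowing will be done other than what is specified for Baseline and worst post-baseline above". The only visits it keeps out of by-visit output are unscheduled ones: "Unscheduled visits will not be included in the by-visit summary or analyses".

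Section 2.1 says that follow-up "will conclude at the end of follow-up (EOFU) visit on Day 33 (28 days after the last dose of study treatment"). Section 4.1 gives the window of "the last planned study visit (Day 33 ± 1 day").

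The footnotes to the schedule in Appendix 14.1 cover early leavers:

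- **Footnote e:** a subject who discontinues the study before Day 33 comes back within 24, and at most 48, hours for the EOFU procedures.
- **Footnote g:** calls this an EOFU visit. It requires labs, vital signs and ECG there only from subjects who left before Day 5, or after Day 5 and before Day 14.

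NP swabs and serology are marked at EOFU without that restriction. The schedule has no separate early-termination visit.

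Sections 8.2.7 and 8.2.8 analyse change in RNA and infectious viral load at Days 3, 5, 9, 14 and 33, and Section 8.3.7 analyses serostatus at Day 33. Sections 7.2, 7.3 and 7.4 summarise labs, vital signs and ECG by visit. The primary endpoint in Table 1 includes "clinical laboratory results, and vital signs through Day 33".

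**The concern.** An exit visit is a named protocol visit, so the exclusion of unscheduled visits does not clearly remove it. With no windowing, its records keep the EOFU label, and EOFU is Day 33. A swab taken on Day 7 from a subject who has just withdrawn would then count as a Day 33 viral load, and the serology sample from that day as Day 33 serostatus. The ANCOVA in Section 8 adjusts for treatment, strata and baseline value, but not for the day of sampling.

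The safety tables have a related problem. Completers are not required to have labs, vital signs or ECG at EOFU. A by-visit EOFU row for these measures would look like the Day 33 safety result, but would describe a small, selected group measured in the first two weeks or so.

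These outputs are not affected: time to TND (uses dates), viral load AUC (actual sampling times), diary endpoints (actual day), adverse event tables and worst post-baseline summaries.

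**Working it through.** The SAP gives no figure on this point to reproduce. The check is date arithmetic plus a scale calculation.

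**1. When exit EOFU records fall.** Leaving day is 1 to 32 (before Day 33), and the visit follows 0 to 2 days later (footnote e).
- Earliest: 1 + 0 = Day 1. Latest: 32 + 2 = Day 34.
- Planned window: 33 ± 1 = Days 32 to 34.
- Off-window exit days are therefore Days 1 to 31, which are 33 − 31 = 2 to 33 − 1 = 32 days early.
- Exit visits on Days 32 to 34 do no harm. Only subjects leaving on Days 30 to 32 can reach that window.

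**2. EOFU labs, vital signs and ECG (footnote g).**
- Left on Days 1 to 4: visit on Days 1 to 6.
- Left on Days 6 to 13: visit on Days 6 to 15.
- Together Days 1 to 15, which is 33 − 15 = 18 to 33 − 1 = 32 days early. None lies in the Day 33 window.

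**3. Whether another rule redirects these records.**

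| SAP section | What it governs | Assigns a visit to an exit record? |
|---|---|---|
| 3, missing row: "will be included in count tabulations as needed to account for dropouts and missing values" | Count tables | No |
| 3.4.3, ITT-c: "and with at least one post-baseline primary efficacy measurement" | Population; leavers can be included | No |
| 3.4.4, PP exclusion: "Do not complete Day 33 Visit (discontinuation from study prior to Day 33 or incomplete follow-up at the time of analysis") | Population; Section 8.1.2 uses PP only for the primary efficacy analyses | No |
| 8, censoring | Time-to-event endpoints only | No |

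**4. Scale of the effect on viral load.** Let f be the share of an arm's Day 33 values that are off-window exit swabs, and g the mean log10 gap between those values and true Day 33 values. The arm mean shifts by f × g. With a common gap, the unadjusted arm difference shifts by (difference in f) × g. The SAP gives neither input. Assume a difference in f of 0 to 5 percentage points and g of 1 to 4 log10:
- 1 point and 1 log10: 0.01 × 1 = 0.01 log10.
- 5 points and 4 log10: 0.05 × 4 = 0.20 log10.
- Equal shares and gaps: 0.

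For serostatus, an arm's Day 33 seropositive percentage cannot move by more than its share of off-window exit samples.

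**5. Whether the proposed rule places every off-window day.** With the schedule's windows (Day 3, Day 5, Day 9 ± 1, Day 14 ± 1):
- Days 3, 5, 8–10 and 13–15 match an earlier visit: 1 + 1 + 3 + 3 = 8 days.
- Days 1–2, 4, 6–7, 11–12 and 16–31 do not: 2 + 1 + 2 + 2 + 16 = 23 days.
- 8 + 23 = 31, so every off-window day is assigned.

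**The case against.** The strongest reply is that the SAP never says that visit labels decide the analysis visit. Section 3.4.4 treats someone who leaves early as not having completed the Day 33 visit, Section 8 separates the two groups for censoring, and Sections 8.2.7 and 8.2.8 name time points by day. A programmer could reasonably decline to call a Day 6 exit swab Day 33. The eCRF visit coding is not shown, and parts of the SAP, including Section 3.2, are blacked out, so the absence of a rule cannot be fully confirmed. This stands as a limit: retention of the label is inferred. But those sections settle population membership and censoring. None says where an existing exit record goes, and the one visible rule on visits rules out reassigning it.

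Second, no Day 33 safety comparison is displaced, because none is planned for completers; the small n would be visible, and Section 7.2 limits lab summaries to scheduled visits. That is fair, and it lowers the risk of misreading. The row would still carry the EOFU label.

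Third, the size rests on assumptions. The 0.20 log10 pairs both upper values, an exit on Day 31 may differ from Day 33 by less than 1 log10, and a seronegative exit sample leaves the summary percentage where a missing one would. All of this stands.

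Fourth, subjects who stop treatment on Days 1 to 3 but stay in the study have their EOFU on Days 29 to 31 (last dose day + 28), also outside Day 32 to 34. Those are planned visits, since Section 2.1 also defines EOFU as 28 days after the last dose. They are not exit records and need no change here.

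**Conclusion.** The concern holds. Applied as written, the plan puts exit swabs and serology from as early as Day 1 into Day 33 results, and any EOFU row for labs, vital signs or ECG would consist essentially of subjects who left before Day 14. Off-window exit samples are 2 to 32 days early; the EOFU safety measures are 18 to 32 days early.

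The effect is confined to the Day 33 time point of two secondary viral load endpoints, Day 33 serostatus, and the by-visit safety tables. Arm-level values are distorted in any arm with off-window exit records that differ from true Day 33 values. The comparison between arms is biased only if the share of exit records or their gap from Day 33 differs between arms. The 0 to 0.20 log10 range is for scale only and rests wholly on the assumed inputs. Confidence is medium, because retention of the EOFU label is inferred. This should be settled before unblinding, since it decides how dropout records are handled.

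**What to change.** Add one exception to the no-windowing rule in Section 3, along these lines:

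> EOFU records of subjects who discontinue the study before Day 33 are not analysed as Day 33 unless collected on Day 32 to 34. By actual study day, they are assigned to the scheduled visit whose planned window contains that day (Day 3, Day 5, Day 9 ± 1, Day 14 ± 1), only if that visit has no scheduled record for the assessment. All others are assigned to a separate Early Termination visit.

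Then:

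- **Serology:** apply the same rule. There is no scheduled sample between Day 1 and Day 33, so off-window exit samples go to Early Termination and the subject counts as missing at Day 33.
- **Labs, vital signs and ECG under footnote g:** show them as Early Termination, or at the matching earlier visit if it is empty, and not as a Day 33 row. Keep them in listings and in worst post-baseline summaries where these are planned.
- **All other visits:** leave as labelled.

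The cost is one paragraph and a small programming step, with no new data. There will be slightly fewer Day 33 values and one extra visit label in the by-visit tables.

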3.1. Incomplete and Missing Data

Imputation rules for missing dates of prior/concomitant medications, including COVID-19 vaccinations and prohibited medications, and procedures are provided in [Appendix 14.5](#).

Imputation rules for missing AE data are provided in [Appendix 14.5](#).

Data that are continuous in nature but are reported in the form $<x$, $>x$, $\leq x$, or $\geq x$ (where x is considered as the limit of quantitation) will be set to limit of quantitation value with the following exceptions:

- Efficacy endpoint data will be imputed as detailed in [Appendix 14.5](#).
- PK concentrations data will be imputed as detailed in [Appendix 14.5](#).

- Other incomplete/missing data will not be imputed, unless specified otherwise.

All analyses will be conducted using SAS Version 9.4 or higher. Unless otherwise stated, a two-sided test will be used at a significance level (alpha) of 0.05 for all analyses. Two-sided 95% confidence intervals (CI) will be provided when appropriate.

Summary Tables and Figures will be presented by treatment group and will be labelled as follows:

- “EDP 235 [REDACTED]”
- “EDP 235 [REDACTED]”
- “Placebo”

All subject data will be presented in individual subject data listings. Dates will be shown in subject listings as they have been recorded. Unless otherwise stated, unscheduled visit results will be included in date/time chronological order, within subject listings only. All listings will be sorted by subject number, date/time and visit. The treatment group (randomized) as well as subject’s sex and age will be stated on each listing. Unless otherwise stated, data listings will be based on all subjects randomized.

When no data are available for a table or listing, an empty page with the title will be produced with suitable text (e.g., “There are no records for this table/listing.”). For analyses where convergence or the analysis cannot be performed, “NC” (not calculable) will be presented in summary tables.

For the reporting of this study both CDISC SDTM (SDTM Implementation Guide version 3.3 or later) and ADaM (ADaM Implementation Guide version 1.3 or later) standards will be applied.

[REDACTED]

[REDACTED]

3.3. Randomization, Stratification, and Blinding

Subjects who have completed screening assessments and are eligible for participation in the study will be randomized to blinded treatment before the first dose of study treatment (Day 1) in a 1:1:1 ratio to receive either EDP 235 [REDACTED], EDP 235 [REDACTED], or placebo orally once daily for 5 days. Randomization will be stratified by age (≤ 50 years or 51 to 64 years) and the duration of COVID-19 symptoms (≤ 3 days or >3 days and ≤ 5 days).

The study will be double-blinded, meaning that the subjects, investigators, and site staff will be blinded to treatment assignment until the completion of the study. During the study, investigators, site personnel, and blinded contract research organization/Sponsor staff will not have access to results for individual subjects that could impact clinician assessments, including results for SARS-CoV-2 viral load, respiratory pathogen panel testing, certain biomarkers, and PK.

The unblinding method will use the IWRS process which will allow the investigator to have immediate access to the unblinding system. Unblinding of individual subject treatment by the investigator should be limited to medical emergencies or urgent clinical situations in which knowledge of the subject's study treatment is necessary for clinical management. In situations where the urgency of the case requires immediate action, investigators should use their best judgment, based on the nature and urgency of the clinical situation, and proceed with unblinding. In emergency situations, the decision to unblind resides solely with the investigator.

Once a subject's treatment assignment has been unblinded for a medical emergency or urgent clinical situation, the [REDACTED] Medical Monitor should be notified within 24 hours of unblinding of the treatment and should inform the Sponsor's Medical Monitor.

3.4. Analysis Populations

3.4.1 Randomized Population

The Randomized Population includes all subjects who are randomized.

3.4.2. Safety (SAF)

The Safety Population includes all subjects in the Randomized Population who receive at least one dose of the study treatment. Subjects will be analyzed in the treatment group that corresponds to the study treatment received during the study.

